10.2.4 Timing of Assessments to Determine Response

Disease assessments will be made at the end of Cycle 2 and every two cycles thereafter. Disease assessments may be made at other time points at the discretion of the Investigator.

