Blood samples for PK assessment of FF-10502 plasma concentrations for patients in Cohort 13 will be collected on Cycle 1 Days 1 and 8, pre-dose, immediately following cessation of infusion (within 15 minutes), between 1-2 hours post-infusion, and between 4-6 hours post-infusion. Incorporation of FF-10502 into the cellular DNA of whole blood will be assessed as a pharmacodynamic endpoint pre-dose on Cycle 1 Days 1 and 8; and at any time during the Cycle 1 Day 15 visit. Blood for hematology and serum chemistry determinations will be collected within 28 days before Cycle 1 Day 1, on Days 1, 8, and 15 of Cycle 1, on Day 1 of each subsequent cycle, and at End of Treatment. After Cycle 1, blood for hematology also will be collected pre-dose on Day 8 of each cycle. Urine will be collected for urinalysis within 28 days before Cycle 1 Day 1, on Day 1 of each cycle, and at the End-of-Treatment Visit.

All Cohorts (Both Phases):

Disease assessments, based on computed tomography (CT) and/or magnetic resonance image (MRI), will be obtained at Week 8 and every 8 weeks thereafter until documented progression of disease (PD) for Cohorts 1 to 12; and at Week 6 and every 6 weeks thereafter until documented PD for Cohort 13. Patients who demonstrate clinical benefit will be allowed to continue therapy with FF-10502-01 until progression of disease, observation of unacceptable adverse events, intercurrent illness or changes in the patient's condition that prevents further study participation.

Safety will be assessed through the monitoring of AEs, clinical laboratory parameters (hematology, serum chemistry), vital sign measurements, and physical examinations. Adverse events will be classified according to the Medical Dictionary for Regulatory Affairs (MedDRA) and graded according to the National Cancer Institute Common Terminology Criteria for Adverse Events (NCI CTCAE) version 4.03.

Efficacy assessments for solid tumors will be made according to the Response Evaluation Criteria in Solid Tumors (RECIST v. 1.1)¹.

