8.2 Study Drug Administration

Patients should be scheduled to begin study therapy following completion of Screening.

FF-10502-01 is compatible with both dextrose 5% in water (D5W) and 0.9% sodium chloride (normal saline; NS) when diluted to a final concentration between 50 µg/mL and 1.5 mg/mL. After admixture, the final IV admixture may be maintained at room temperature or under refrigeration (2-8°C) for up to 24 hours. The infusion will be administered over a 1-hour period.

Phase 1: Patients will receive FF-10502-01 weekly IV at the dose level prescribed per cohort on Days 1, 8 and 15 of each 28-day cycle (= 1 cycle).

Phase 2a, Cohorts 10 to 12: Patients will receive FF-10502-01 90 mg/m² IV on Days 1, 8 and 15 of each 28-day cycle (= 1 cycle).

Phase 2a, Cohort 13: Patients will receive FF-10502-01 90 mg/m² IV on Days 1 and 8 of each 21-day cycle (= 1 cycle).

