8.4.2 Instructions Regarding Dose Delays and Dose Modifications

Adverse events considered for treatment interruption and dose reduction will exclude the events assessed by the investigator as exclusively related to underlying disease or medical condition/concomitant treatment. If treatment must be delayed for reasons other than toxicity, contact the Medical Monitor to discuss the reasons for delay and plans for resuming study therapy.

- Treatment may be delayed up to 14 days. If the patient has completed two cycles and, in the investigator's opinion, is receiving benefit, treatment may be delayed for longer than 14 days and then resumed following a discussion with the Medical Monitor. Patients who require the next treatment cycle to be held for more than 14 days due to ongoing toxicity from the prior cycle should have the dose reduced by 25%.

- Patients who experience a toxicity requiring reduction in dose level may continue treatment at the lower dose level until disease progression or unacceptable toxicity. The dose level may be reduced twice. Patients who continue to require dose modifications beyond this should be discontinued from the trial. Once the dose has been reduced it may not be escalated.
- See [APPENDIX C](#) for FF-10502-01 dose modification requirements.

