9.2.2 Requirements During Treatment Cycles After Cycle 1 (Cycles 2, 3, 4, etc)

9.2.2.1 Day 1 of Each Cycle (± 2 days)

- Abbreviated physical examination
- Vital signs
- ECOG Performance Status
- Weight
- The following lab tests (within 3 days of each cycle – see [Table 3](#) for a list of lab tests):

- Hematology. Note: In addition to total lymphocyte counts, T cell (CD4 and CD8) and B cell counts will be obtained.
- Serum chemistry
- Urinalysis
- Review of concomitant medications
- Assessment of AEs
- Administration of FF-10502-01 over a 1-hour period

9.2.2.2 *Day 8 of Each Cycle (±2 days)*

- The following lab tests (see [Table 3](#) for a list of lab tests):
 - Hematology
- Review of concomitant medications
- Assessment of AEs
- Administration of FF-10502-01 over a 1-hour period

9.2.2.3 *Day 15 of Each Cycle (±2 days) [Cohorts 1 to 12 only]*

- The following lab tests (see [Table 3](#) for a list of lab tests):
 - Hematology
- Review of concomitant medications
- Assessment of AEs
- Administration of FF-10502-01 over a 1-hour period

9.2.2.4 *End of Cycle 2 and Every 2 Cycles Thereafter (±3 days)*

- Disease-specific assessment (CT, MRI scans)
- Review of concomitant medications
- Assessment of AEs

9.3 **At Relapse or Progression of Disease**

- Disease-specific assessment (CT, MRI scans)
- Review of concomitant medications
- Assessment of AEs

9.4 **End of Treatment (28 days, ± 5 days, from the last dose of Study Drug)**

- Physical examination
- Vital signs
- ECOG Performance Status
- Weight
- The following lab tests: (See [Table 3](#) for a list of lab tests)

- Hematology. Note: In addition to total lymphocyte counts, T (CD4 and CD8) and B cell counts will be obtained at end of treatment.
- Serum chemistry
- Urinalysis
- 12-lead ECG
- Review of concomitant medications
- Assessment of AEs

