11.3.2 Efficacy Analyses

11.3.2.1 Primary Efficacy Endpoint

The primary efficacy endpoint is the proportion of patients in each disease cohort (cholangiocarcinoma, gallbladder carcinoma, urothelial carcinoma, or other solid tumor) with objective response (OR) within 4 cycles of study drug. Thus, this is the proportion of patients in Cohorts 1-12 with an OR within 16 weeks of their first dose of study drug and the proportion of patients in Cohort 13 with an OR within 12 weeks of their first dose of study drug. The OR rate is defined as the proportion of patients in the FAS with a confirmed complete or partial response. Ninety percent confidence intervals for the OR rate will be estimated.

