- **Progressive Disease (PD):** Unequivocal progression of existing non-target lesions, or appearance of one or more new lesions. When the patient also has measurable disease, to achieve 'unequivocal progression' on the basis of non-target disease, there must be an overall level of substantial worsening in non-target disease such that, even in the presence of SD or PR in target disease, the overall tumor burden has increased sufficiently to merit discontinuation of therapy.
- **Not Evaluable:** One or more Non-Target Lesions could not be assessed.

Overall Response

At each protocol-specified time point (Day 28 of every 2nd cycle for Cohorts 1-12; and day 21 of every 2nd cycle for Cohort 13), an overall response assessment is made by the PI. Criteria for overall response for target and non-target disease are summarized in the table below:

Overall Response for Target and Non-Target Disease

	Target Lesion	Non-Target Lesion	New Lesions
Complete Response (CR)	CR	CR or NA	No
Partial Response (PR)	CR	Non-CR/Non-PD	No
	CR	Not evaluated	No
	PR	Non-PD or not all evaluated	No
Stable Disease (SD)	SD	Non-PD or not all evaluated	No
Progressive Disease (PD)	PD	Any	Yes or No
	Any	PD	Yes or No
	Any	Any	Yes
Not Evaluable (NE)	Not all evaluated	Non-PD	No

Best Overall Response

The Best Overall Response is the best response across all protocol time points.

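### Scans are scheduled by calendar week in some sections and by treatment cycle in others, and the response endpoint treats the two as equal, so after a dose delay the second scan can fall past Week 16 (Week 12 in Cohort 13)

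*Protocol*

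**What the plan says.** **Calendar rule.** Protocol 6.1 says that scans "will be obtained at Week 8 and every 8 weeks thereafter until documented progression of disease (PD) for Cohorts 1 to 12". The urothelial cohort has its own interval in the same section. The Synopsis and SAP 1.3.2 agree, and for that cohort the interval is 6 weeks, starting at Week 6.

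**Cycle rule.** Protocol 10.2.4 says "Disease assessments will be made at the end of Cycle 2 and every two cycles thereafter". Protocol 9.2.2.4 is headed "End of Cycle 2 and Every 2 Cycles Thereafter (±3 days"), and Tables 6 and 7 in Appendix D follow it. SAP 3.3.1 places the assessment at "Day 28 of every 2nd cycle for Cohorts 1-12; and day 21 of every 2nd cycle for Cohort 13".

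**Endpoint limit.** Protocol 11.3.2.1 and SAP 3.3.1 define the primary efficacy endpoint as objective response within four cycles, then restate it: "Thus, this is the proportion of patients in Cohorts 1-12 with an OR within 16 weeks of their first dose of study drug" (12 weeks for Cohort 13). Protocol 10.2.3.1 gives weeks only. The planned table in SAP 4.1.4 gives cycles only.

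**Delays.** Protocol 8.4.2 says "Treatment may be delayed up to 14 days". After two completed cycles with benefit, it allows longer delays following discussion with the Medical Monitor, with no stated maximum. Appendix C repeats this.

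**Confirmation and visit labels.** The response must be confirmed (Protocol 11.3.2.1). Protocol 10.2.2.1 asks for confirmation 28 days later. SAP 2.3.1.1 applies no visit windows and uses the visit label on the case report form.

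**The concern.** Neither document says which scan rule governs once a cycle start has slipped, nor whether the endpoint limit is then counted in cycles or weeks. If scans move with the cycles while the limit stays fixed in weeks, ascertainment of response depends on how well the patient tolerates treatment. A patient with a toxicity delay may have one scan inside the limit where an undelayed patient has two. Scan-detected progression can also be dated later in the delayed patient, which affects progression-free survival, duration of response and duration of stable disease. The status of a response first seen at the second scan is unclear even without a delay, because its confirmation falls after the limit.

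**Working it through.** **Inputs**
- Cycle length L: 28 days (Protocol 8.2: "Patients will receive FF-10502-01 90 mg/m² IV on Days 1, 8 and 15 of each 28-day cycle (= 1 cycle"); 21 days in Cohort 13.
- Endpoint limit: Week 16, Day 112; Week 12, Day 84 in Cohort 13. The first dose is taken as Day 1 and Week 16 as ending on Day 112. If the limit is read as 112 (84) days elapsed after the first dose, it becomes Day 113 (85) and the thresholds below move by one day.
- Scan window: ±3 days (Protocol 9.2.2.4; Tables 6 and 7). Next Day 1: ±2 days (Protocol 9.2.2.1; Tables 6 and 7).
- D: net slip of the cycle calendar by the end of Cycle 4. A dose omitted within a cycle that does not move the next cycle gives D = 0.

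**Step 1. The plan's own equivalence, no delay.** First scan: 2 × 28 = 56 days (Week 8) and 2 × 21 = 42 days (Week 6). Second scan: 4 × 28 = 112 days (Week 16) and 4 × 21 = 84 days (Week 12). The stated figures reproduce, and the second scan falls exactly on the limit with no slack.

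**Step 2. Second scan under the cycle rule: 4L + D, window ±3 days.**

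| Net delay D | Cohorts 1-12: nominal (window) | Cohort 13: nominal (window) | Earliest scan past limit? |
|---|---|---|---|
| 0 | 112 (109-115) | 84 (81-87) | No |
| 3 | 115 (112-118) | 87 (84-90) | No |
| 4 | 116 (113-119) | 88 (85-91) | Yes |
| 7 | 119 (116-122) | 91 (88-94) | Yes |
| 14 | 126 (123-129) | 98 (95-101) | Yes |

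A single 14-day delay gives Week 18 (14). With no delay at all, the late side of the window already permits Day 115 (87).

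**Step 3. First scan.** A 14-day delay at the start of Cycle 2 moves it to 56 + 14 = Day 70 (42 + 14 = Day 56 in Cohort 13), still inside the limit. The responses exposed are therefore those first seen at the second scan.

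**Step 4. Progression.** A delay of d days between two scans lengthens that interval from 56 (42) to 56 + d (42 + d) days. With d = 14 it is 70 (56) days. Progression already present on the calendar scan date is dated later by the accumulated delay.

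**Step 5. Confirmation.** A response first seen at Week 16 (12) is confirmed at 16 + 4 = Week 20 (12 + 4 = Week 16) without any delay.

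**Step 6. Overlapping windows.** The end-of-Cycle-2 scan may fall on Days 53-59. Cycle 3 Day 1, nominally Day 57, may fall on Days 55-59. The scan can thus come up to 59 − 55 = 4 days after the next dose. In Cohort 13 the ranges are Days 39-45 and 41-45, again up to 4 days.

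**The case against.** Several points on the other side stand in part.

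- Protocol 10.2.4 also allows scans at other times at the investigator's discretion, and Protocol 9.3 adds one at progression. These soften the effect. The first is optional and the second is triggered by an event, so neither is a fixed schedule.
- If the four-cycle wording governs, as the SAP 4.1.4 table title and the visit-label rule in SAP 2.3.1.1 suggest, a delayed end-of-Cycle-4 scan counts and no response is lost. That reading is available, but Protocol 11.3.2.1 and SAP 3.3.1 go on to spell out weeks. The defect is therefore an ambiguity.
- The 3-day window absorbs small slips. Best overall response in SAP 3.3.1 still captures late responses. The time-to-event endpoints are secondary, single-arm and descriptive, and the primary objective is safety and dose finding.
- Later dating of progression is not uniform. Progression arising between the calendar date and a displaced scan is found sooner than at the next calendar scan.

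A reader might infer more than this:

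- **A share of patients affected.** Compounding an assumed delay rate over three cycle starts would treat every patient as starting Cycles 2 to 4. The documents give no delay rate.
- **A loss of power in Cohorts 11 and 13.** An exact calculation with the two-stage rules in Protocol 11.1 taken as binding gives 80.7% and 81.0%. If 10% of true responders went uncounted (assumed), response rates of 16% × 0.9 = 14.4% and 20% × 0.9 = 18% would give 71.7% and 73.4%. Over an assumed 5% to 30%, power runs from 76.5% to 46.9% and from 77.5% to 52.7%. The documents supply no such share, and Protocol 11.1 does not apply the week limit to its response counts.
- **Sites that cannot be compared.** No comparison between sites is planned.

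**Conclusion.** The contradiction is real, stands in the current text of both documents, and should be fixed. Under the cycle rule with the week-based limit, a net delay of 4 days or more by the end of Cycle 4 puts the second scan after Day 112 (84). A response first seen there may not count, and progression may be dated later by up to the accumulated delay. This rests on the day count stated in the working and on a slip of the cycle calendar itself. It does not show that responders will be lost: that depends on which wording prevails, on discretionary scans, and on delay frequency. The number of patients affected cannot be computed from the documents.

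**What to change.** 1. In Protocol 9.2.2.4, 10.2.4, Tables 6 and 7, and SAP 3.3.1, adopt the calendar schedule already in Protocol 6.1 and SAP 1.3.2: Weeks 8, 16, 24 and so on for Cohorts 1-12, and Weeks 6, 12, 18 and so on for Cohort 13, counted from first dose regardless of dose delays. Check SAP Appendix A for the same wording.
2. State the endpoint limit once, in weeks, in Protocol 10.2.3.1 and 11.3.2.1 and in SAP 3.3.1 and 4.1.4. Say that a scan within the permitted window of the Week 16 (12) visit counts.
3. State that a response first documented by that visit counts if it is confirmed at least 28 days later, even when the confirmation falls after the limit.
4. The sponsor should reconcile the overlapping scan (±3 days) and next Day 1 (±2 days) windows. No particular window is proposed here.

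The cost is amendment and SAP wording, with no more scans per unit of time than the calendar rule already requires. The small downside is that in a delayed patient the scan may not coincide with a cycle-end visit.

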10.2.5 Pharmacokinetic Endpoints

Because a limited number of plasma concentrations will be determined, full determination of routine PK parameters may not be possible. In addition to mean plasma concentrations, as the data allow, additional PK analyses will be provided (trough levels, $t_{1/2}$, T_{max} , C_{max} , AUC, etc). In Phase 2a expansion, population PK methods will be utilized to characterize the PK profile of FF-10502.

10.2.6 Pharmacodynamic Endpoints

FF-10502 incorporation into whole blood cellular DNA is expected to increase following treatment in a dose dependent manner, based on mechanism of action. Therefore, as a measure of pharmacologic activity and a preliminary measure of efficacy, FF-10502 incorporation into the cellular DNA of whole blood will be assessed and correlated with clinical outcome.¹⁸ In the Phase 2a expansion, PD data will be combined with PK data to assess the impact of drug exposure on FF-10502 incorporation into DNA.

11 STATISTICAL METHODOLOGY

11.1 Determination of Sample Size

Phase 1:

The sample size reflects requirements associated with a single patient dose escalation until \geq Grade 2 toxicity is observed, thereafter a 3+3 design. A total of 3 to 54 patients are planned (1 to 6 patients in each of 9 dose cohorts).

Phase 2a:

There are 4 cohorts in Phase 2a. The expansion cohorts will assess the efficacy of FF-10502-01 in a cohort of patients with a variety of solid tumors (Cohort 10), in a cohort of patients with cholangiocarcinoma (Cohort 11), in a cohort of patients with gallbladder carcinoma (Cohort 12), and in a cohort of patients with urothelial carcinoma (Cohort 13).

The primary measure of efficacy in these 4 expansion cohorts will be response according to the RECIST 1.1. criteria. A maximum of 20 patients will be accrued in Cohort 10, a maximum of 50 patients will be accrued in Cohort 11, a maximum of 10 patients will be accrued in Cohort 12, and a maximum of 27 patients will be accrued into Cohort 13.

Cohort 10: Cohort 10 will recruit patients with a variety of solid tumors to explore whether responses are seen in additional tumor types. If the overall response rate amongst these patients is 14%, there will be a less than 5% chance of failing to see a response in at least 1 patient.

Cohort 11 (cholangiocarcinoma): Historically, very low response rates have been observed in cholangiocarcinoma. Cohort 11, with a maximum of 50 patients, has 80% power if the true response rate, p_1 , is 16%, using a 1-sided type I error of 5% with a null hypothesis, p_0 , of 5%. A Simon 2-stage design will be employed so that 50 patients are only recruited if evidence of activity is confirmed at an interim analysis. If after 25 patients have been recruited, there are 1 or fewer responses, enrollment for this cohort may be suspended for futility. If after 50 patients have been recruited, 6 or more responses are observed, the null hypothesis of a 5% response rate will be rejected. An alternative analysis may include all treated cholangiocarcinoma patients—not just those meeting the definition of Cohort 11.

Stable disease for ≥ 4 cycles (approximately 4 months) may also be of clinical benefit in this population. If the proportion of patients in this cohort having stable disease is $\geq 30\%$ after 25 patients have been enrolled and treated, enrollment into this cohort may continue until 50 patients are treated. Note that recruitment will continue past 25 patients—it will not stop until a decision is made at the interim analysis.

Cohort 12 (gallbladder carcinoma) is exploratory with 10 patients to be recruited. If the response rate amongst these patients is 26%, there will be a less than 5% chance of failing to see a response in at least 1 patient.

Cohort 13 (urothelial carcinoma) will also employ a Simon 2-stage design with 80% power, a 1-sided type I error of 5%, $p_1 = 20\%$ and $p_0 = 5\%$. If after 15 patients have been recruited, there are no responses, enrollment for this cohort may be suspended for futility. If after 27 patients have been recruited, 4 or more responses are observed, the null hypothesis of a 5% response rate will be rejected.

In both Cohorts 11 and 13, there will be no pause in recruitment prior to the interim analysis given the previous responses already observed in these indications. Furthermore, prior to any

decision to stop recruitment into a given cohort, the number of patients with prolonged stable disease will also be considered.

11.2 Analysis Populations

The safety analysis set includes all patients who are administered any fraction of a dose of study drug. For a particular measure, the full analysis set (FAS) includes those patients who have a valid baseline and one or more post-treatment assessments for that measure of interest.

The PK population consists of all patients in the FAS who complete a baseline and at least one follow-up PK assessment.

The pharmacodynamic () population consists of all patients in the FAS who complete a baseline and at least one follow-up pharmacodynamic assessment.

11.3 Statistical Analysis Methods

All data will be analyzed using Statistical Analysis System (SAS Version 9.4 or higher for Windows, SAS Institute, Cary, NC). Continuous variables will be summarized using number, mean, standard deviation, median, minimum, and maximum. Categorical variables will be summarized using number and frequencies.

11.3.1 Safety Analyses

11.3.1.1 Adverse Events

All safety endpoints will be summarized using descriptive statistics and will be based on the safety analysis dataset.

All AEs will be coded based on the Medical Dictionary for Regulatory Affairs (MedDRA; Version 15.0 or higher). An AE will be considered a treatment emergent adverse event (TEAE) if the onset is after the first dose of study drug to 28 days following the last dose of study drug or if the condition was present at baseline but worsened after the first dose.

All AEs for each patient will be listed, including intensity grading, relationship to study drug, action taken and outcome. Patient listings of deaths, SAEs, and AEs leading to treatment discontinuation will be provided. Patient narratives will be provided for deaths, SAEs and other significant AEs. Summary tables will be prepared to examine TEAE severity and relationship to study treatment.

AE summaries will be produced separately for each dose cohort and overall, and each disease cohort by dose and overall. All summaries will show, dose cohort and overall, the number and percentage of patients experiencing at least 1 TEAE of each preferred term, arranged by system organ class, and the number of occurrences of the event. Separate summaries will be produced by relationship to study drug, by severity, and for those events with an incidence rate of at least 2% in any group or overall.

SAEs will be summarized in a similar manner; overall, by relationship to study drug, and by severity.

In addition to the above, summaries of the number and percentage of patients discontinuing the study due to AEs and, due to death, will be presented.

